7.3.2 Lens Performance Assessment Visit (Part B)

The subjects should attend this visit wearing their spectacles, not having worn their own contact lenses for a minimum of 12 hours prior to this visit.

1. Details of ocular history and contact lens wearing history will be checked for any changes since the last visit.
2. Baseline distance high contrast logMAR visual acuity (OD, OS) with spectacles or habitual Rx in phoropter or trial frame
3. Slit lamp biomicroscopy will be assessed according to the guidelines set out in the CVI Grading scales (Appendix 1).
4. Saline Rinse

7.3.3 Lens Pair 1

7.3.3.1 Lens Insertion

1. The first lens pair, manufactured from information obtained in Part A, will be fitted according to the randomization table.
2. Lenses will be allowed to settle for at least 15 minutes.

7.3.3.2 Visual Acuity / Lens Fitting

1. Binocular and monocular visual acuity will be assessed at distance (equivalent to 6M) and near (40cm) before over-refraction:
 - HIHC* logMAR VA (equivalent to 6M, 40cm) – (OD, OS, OU)

2. [REDACTED]

[REDACTED]

[REDACTED]

[REDACTED]

[REDACTED]

- [REDACTED]

- [REDACTED]

- [REDACTED]

[REDACTED]

[REDACTED]

- [REDACTED]

- [REDACTED]

- [REDACTED]

- [REDACTED]

7.3.3.5 Contact lenses to be removed by investigator and retained for return to the Sponsor.

7.3.4 Lens Pair 2 and Exit

1. The second lens type will be inserted according to randomization schedule.
2. The same procedures outlined in Section 7.3.3 will be repeated.
3. Subjects to assess their preference between Lens Pair 1 and 2 for a number of considerations according to the CVI guidelines in Appendix 3 (5 point Likert scale) (Strong Pair 1, Slight Pair 1, no preference, Strong Pair 2, Slight Pair 2):
 - [REDACTED]
 - [REDACTED]
 - [REDACTED]
 - Overall Vision Preference
 - [REDACTED]
 - [REDACTED]
 - [REDACTED]
4. Contact lenses to be removed by investigator and retained for return to the Sponsor.
5. Slit lamp biomicroscopy will be assessed according to the guidelines set out in the CVI Grading scales (Appendix 1).
6. Exit high contrast logMAR visual acuity (OD, OS) with spectacles or habitual Rx in phoropter or trial frame
7. The subject will be discharged and asked to sign the exit statement.

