CooperVision™

Study Implementation document: Protocol

CLINICAL EVALUATION OF BIOFINITY MULTIFOCAL TORIC CONTACT LENSES

Sponsor Study Code: CV-18-11
Version Number: 1.0
Implementation document Date: 21 Feb 2018
Sponsor Company: CooperVision, Inc.
Document Type: Protocol
Study Category: [REDACTED]
Clinical Sites: [REDACTED]
Site Protocol Number: C17-634

Study Sponsor Representative: _____ **Date:** _____
[REDACTED]

CooperVision Sponsor Management: _____ **Date:** _____
[REDACTED]

Site Principal Investigator: _____ **Date:** _____
[REDACTED]
[REDACTED]

Confidential

TABLE OF CONTENTS

1	Introduction	5
2	Study Objective	5
2.1	Study Hypothesis.....	5
3	Study Design	5
4	Ethics Review / Statement of Compliance	6
4.1	Relevant Standards / Guidelines.....	6
4.2	Institutional Review Board.....	6
4.3	Informed Consent	6
5	Clinical Trial Registration	7
6	Potential Risks and Benefits to Human Subjects	7
7	Materials and Methods	8
7.1	Subjects	8
7.2	Study Materials	9
7.3	Visit Schedule and Procedures	11
8	Adverse Event Reporting	16
8.1	Adverse Event Definitions	16
8.2	Procedures for Adverse Events.....	18
8.3	Reporting Adverse Events.....	18
8.4	Discontinuation from the Study	19
9	Device Malfunctions	19
10	Statistical Analysis	20
10.1	Statistical Plan	20
11	Data Quality Assurance	20
11.1	Study monitoring.....	20
11.2	Record keeping.....	21
11.3	Record retention	21
11.4	Data Entry / Data Management.....	21
11.5	Confidentiality	22
11.6	Publication	22
12	Study Costs	22

DOCUMENT CHANGE HISTORY

Version	Originator	Description of Change(s)	Date
1.0	[name]	Original Protocol	21 February 2018

1 Introduction

CooperVision, (CVI) is extending the power range of the commercially available Biofinity silicone hydrogel contact lenses to include multifocal toric silicone hydrogel contact lenses (Biofinity MFT).

This study is to evaluate the clinical performance of the Biofinity MFT lenses.

2 Study Objective

The objective of this non-dispensing clinical study is to compare the clinical performance of Biofinity Multifocal Toric (BF MFT) with Proclear Multifocal Toric (PC MFT) contact lenses.

The primary variable of interest is:

- Visual acuity (VA)

The secondary variable of interest is:

- Subjective assessments of visual performance

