7.1 Subjects

Up to twenty subjects will be needed to complete the study. Each subject will be given a unique ID number. Additionally, all subjects must meet the study inclusion and exclusion criteria listed below. Potential subjects will be identified from the investigators' clinic database records and/or will be actively recruited by advertisements circulated at the investigational sites approved by the appropriate IRB.

Inclusion Criteria

A person is eligible for inclusion in the study if he/she:

- Has had a self-reported oculo-visual examination in the last two years.
- Is aged 40–75 years, inclusive and has full legal capacity to volunteer.
- Has read and understood the participant information sheet.
- Is willing and able to follow instructions and maintain the appointment schedule.
- Is able to participate in Parts A and B related to this work.
- Has a contact lens spherical prescription between +10.00 to -10.00D (inclusive).
- Has an Add component to their spectacle refraction (between +0.75 and +2.50DS).
- Has astigmatism between -0.75 and -5.75DC (based on the vertexed ocular refraction in each eye).
- Can be satisfactorily fitted with the study lenses.
- Is correctable to a visual acuity of 20/40 (0.30 logMAR) or better (in each eye) with their habitual vision correction or 20/25 (0.10 logMAR) best-corrected.
- They have successfully worn soft contact lenses in the last six months
- Has clear corneas and no active ocular disease.
- Has not worn lenses for at least 12 hours before the examination.
- Has an up-to-date pair of spectacles.

Exclusion Criteria

A person will be excluded from the study if he/she:

- Has never worn contact lenses before.
- Has any systemic disease affecting ocular health.

Confidential

- Is using any systemic or topical medications that will affect ocular health.
- Has any ocular pathology or severe insufficiency of lacrimal secretion (moderate to severe dry eyes) that would, in the opinion of the investigator, affect the wearing of contact lenses.
- Has persistent, clinically significant corneal or conjunctival staining using sodium fluorescein dye that would, in the opinion of the investigator, be problematic for their participation in the study.
- Has any clinically significant lid or conjunctival abnormalities, active neovascularization or any central corneal scars.
- Is aphakic.
- Has undergone corneal refractive surgery.
- Has a history of anaphylaxis or severe allergic reaction.

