7.2 Study Materials

7.2.1 Contact Lens

Subjects will be randomized to receive either the Test or Control lens as the first pair of contact lenses as per the randomization schedule. The lenses used in this study will be provided by the Sponsor.

Details of the CE marked contact lenses are shown in Table 1.

Table 1: Study lenses

	Lens 1	Lens 2
Name	Biofinity Multifocal Toric	Proclear Multifocal Toric
Manufacturer	CooperVision	CooperVision
Material	Comfilcon A	Omafilcon B
EWC (%)	48%	62%
Base Curve (mm)	8.7	8.4 / 8.8
Diameter (mm)	14.5	14.4
Spherical powers (DS)	+10.00 to -10.00 (0.50 steps after $\pm 6.50D$)	+20.00 to -20.00 (0.50 steps after $\pm 6.50D$)
Cyl Powers (DC)	-0.75 to -5.75 (0.50 steps)	-0.75 to -5.75 (0.50 steps)
Axis (°)	5 to 180 (5 degree steps)	5 to 180 (5 degree steps)
Add (D)	+1.00, +1.50, +2.00, +2.50 (D & N)	+1.00 to +4.00 (D & N)

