10.1 Statistical Plan

Summary statistics will be produced (e.g. mean, standard deviation). Paired t test will be used to compare slit lamp biomicroscopy, lens fit and subjective scores between study lens types. Repeated Measures Analysis of Variance (ANOVA) or paired analysis will be used to compare the variables between study visits. The critical alpha level for statistical significance will be set at $p \leq 0.05$, with adjustment for multiple comparisons.

All participants who were evaluated will be used in the analysis. In the event of missing data, individual data points will be excluded in the analysis and not extrapolated from the collected data.

11 Data Quality Assurance

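### Does the out-of-order preference scale, answered by wear order, undermine the planned lens comparison?

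*Combined protocol and SAP*

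**What the plan says.** Section 2 makes visual acuity the primary variable and names one secondary variable: "Subjective assessments of visual performance".

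After both pairs have been worn, Section 7.3.4 has this step: "Subjects to assess their preference between Lens Pair 1 and 2 for a number of considerations according to the CVI guidelines in Appendix 3". The five response categories are printed as "Strong Pair 1, Slight Pair 1, no preference, Strong Pair 2, Slight Pair 2". They are labels; no numbers are attached. Overall vision preference is the one item that can be read, the rest being redacted. The same section repeats the Section 7.3.3 procedures for the second pair; these too are partly redacted.

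Section 7.2.1 fixes which lens is Pair 1: "Subjects will be randomized to receive either the Test or Control lens as the first pair of contact lenses as per the randomization schedule".

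Section 10.1 is the whole statistical plan. On subjective data it says: "Paired t test will be used to compare slit lamp biomicroscopy, lens fit and subjective scores between study lens types". It adds: "Repeated Measures Analysis of Variance (ANOVA) or paired analysis will be used to compare the variables between study visits". It does not mention preference, numeric codes, or a conversion from Pair 1/Pair 2 to Biofinity/Proclear. The sample size in Section 7.1 is given as: "Up to twenty subjects will be needed to complete the study".

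**The concern.** Three features look bad together.

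- **Order.** The printed list is not monotone. Numbered 1 to 5 as it stands, a strong preference for Pair 2 scores 4 and a slight one scores 5.
- **Unit.** Each item yields one comparative answer per subject, so there are no two columns of scores to feed a paired t test.
- **Label.** The answer refers to wear order. With order randomised, the mean of raw answers reflects a first-versus-second effect, not a preference for a lens.

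If the answers were scored and averaged this way, a genuine preference on the secondary variable could be reported as none, or an even split could be reported as a tilt.

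**Working it through.** The documents give no effect size, response distribution or power for this item, so there is no stated figure to reproduce. All response mixes below are assumptions. From the documents: n = 20 (the upper limit in Section 7.1), five categories (7.3.4), alpha 0.05 (10.1). Assumed: 10 subjects per sequence and two-sided tests.

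**1. Numbering in printed order.** Correct codes are 1, 2, 3, 4, 5 for strong 1, slight 1, none, slight 2, strong 2. Printed-order codes swap the last two (slight 2 = 5, strong 2 = 4). The error in the mean is therefore

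(number slight 2 − number strong 2) / n.

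Take three symmetric sets of 20, counts given from strong 1 to strong 2 in correct order. The correct mean is 3.0 in each.

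| Counts | Error | Printed-order mean |
|---|---|---|
| 6/2/4/2/6 | (2 − 6)/20 = −0.2 | 56/20 = 2.8 |
| 4/4/4/4/4 | (4 − 4)/20 = 0 | 60/20 = 3.0 |
| 2/6/4/6/2 | (6 − 2)/20 = +0.2 | 64/20 = 3.2 |

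So there is no general tilt towards Pair 1.

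**2. Averaging by wear order.** Suppose all 20 strongly prefer Biofinity, 10 having worn it first. With correct codes the mean is (10×1 + 10×5)/20 = 3.0. With printed-order codes it is (10×1 + 10×4)/20 = 2.5. Both hide a unanimous preference.

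**3. Effect on a test of lens preference.** Code the answers −2 to +2, give them the sign of the lens, and apply a one-sample t test against zero. Simulated rejection rates (20,000 or more replicates), with mixes listed from strong Biofinity to strong Proclear:

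| Assumed mix (%) | Wear order, correct codes | Lens-signed, printed order | Lens-signed, correct order |
|---|---|---|---|
| 40/20/15/15/10 | 3% | 38% | about 50% |
| 20/40/15/15/10 | 4% | about 38% | 35% |
| 15/45/20/15/5 | 3% | 51% | 51% |
| 45/15/20/5/15 | 3% | 51% | 53% |

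The printed order costs power in the first mix, gains a little in the second, and hardly matters in the others. With lens-signed answers and no true preference, type I error stays near 0.05 under either coding (0.047 to 0.054). It rises to about 0.14 only when printed-order codes and wear-order averaging are combined and the strong and slight shares are very unequal (5% against 35% on each side).

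**4. Can the paired t test be used?** Take an invented set of 20: 4 strong Biofinity, 8 slight Biofinity, 4 none, 3 slight Proclear, 1 strong Proclear.

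- Mean = (8 + 8 − 3 − 2)/20 = 0.55.
- Sum of squares = 16 + 8 + 3 + 4 = 31.
- Variance = (31 − 20×0.55²)/19 = 1.313.
- t = 0.55/√(1.313/20) = 2.146, 19 df, p = 0.045.

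Splitting each answer d into +d/2 for one lens and −d/2 for the other and running a paired t test gives the same t and p. Wilcoxon signed-rank gives p = 0.052 here. In simulation under the first mix the two tests had the same power (0.502 for t, 0.498 for Wilcoxon).

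**5. What the text commits to.** Section 7.3.4 assigns no numbers and refers to an Appendix 3 that is not in the supplied text. Section 10.1 does not assign the paired t test to preference. Its subjective scores may be ratings made separately for each lens among the repeated procedures, and a paired t test suits those. The stated contrast is between lens types, not between first and second wear.

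**The case for a change.** The strongest case for acting is that Section 10.1 leaves preference stranded on either reading. If its subjective scores include preference, the raw answers cannot enter a two-column paired test. If they do not, preference has no stated analysis. The wear-order risk is also the serious one: rejection drops from about 35–53% to 3–4% in the mixes above. Correcting the text would cost only a line or two.

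Much of this stands as description. The labels are transposed, the recoding step is unwritten, and no test is named. What does not stand is the harm. An analyst asked to compare lenses in a randomised crossover has to use the randomisation schedule to know which lens each pair was. Averaging wear-order answers would contradict the comparison Section 10.1 asks for. Answers recorded by label keep their meaning whatever order the labels are printed in. Both steps can still be applied after data collection, so nothing is lost irretrievably. Nor did the simulation show any gain from requiring a Wilcoxon test in place of a t test.

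**Conclusion.** The concern does not call for a change. What remains is a transposed pair of labels in Section 7.3.4, which is clerical, and a missing recoding detail in Section 10.1 that any competent analyst would supply from the response labels and the randomisation schedule. The large distortions (a unanimous preference averaging 3.0, or rejection of about 3–4%) arise only if the analyst ignores the lens-type comparison the plan states. The printed-order error alone is ±0.2 of a category or zero in the symmetric examples. For power it ranges from a loss of about 12 percentage points to a gain of about 3 across the assumed mixes.

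This rests on answers being recorded by label, or numbered in sensible order on the form. The supplied text cannot confirm that, because Appendix 3 is absent and parts of 7.3.3 are redacted. The item belongs to the secondary variable; the primary visual acuity comparison is untouched.

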7.3.5 Summary of Visits and Procedures

Table 2 summarizes the visits and procedures for the study.

Table 2: Summary of Visits and Procedures

	Screening/ Baseline visit	Lens fitting and exit visit
Informed Consent	✓	
Meet inclusion/exclusion criteria	✓	✓
Demographics	✓	
History at baseline	✓	✓
VA with spectacles or refraction	✓	✓
Auto-refraction & keratometry	✓	
Pupil size / HVID	✓	
Sphero-cylindrical refraction	✓	

Best corrected (sphero-cyl) logMAR VA monocular and binocular	✓	
Add determination	✓	
Dominant eye test (+2.00 blur test)	✓	
Instillation of lens at office	–	✓
██████████	█	█
logMAR VA with contact lenses	–	✓
██████████		█
Slit lamp findings	✓	✓
██████████ ██████████	█	█
Exit study		✓

8 Adverse Event Reporting

8.1 Adverse Event Definitions

An ‘adverse event’ refers to any undesirable clinical occurrence in a participant, whether it is considered to be device-related or not. Adverse events (AE) may be classified as ‘unanticipated adverse device effects,’ ‘serious adverse events,’ ‘significant adverse events,’ or ‘non-significant adverse events,’ as defined below. All ocular AEs will be recorded and reported to the sponsor, as will any serious non-ocular adverse events .

AE classification, coding (for reporting to the sponsor) and examples are provided in the following table of Contact Lens Adverse Event Classification and Reporting table:

Classification	Definition
Serious Adverse Event	Those events that are life-threatening, or result in permanent impairment of a body function, or permanent damage to a body structure or necessitate medical (therapeutic) or surgical intervention to preclude permanent impairment of a body function or permanent damage to a body structure.
Significant Adverse Event	Those non-serious adverse events that occur with contact lens usage that are not sight-threatening but are usually symptomatic and may warrant therapeutic management and /or temporary or permanent discontinuation of contact lens wear.
Non-Significant Adverse Events	Those less severe non-serious adverse events that occur with contact lens usage that are not sight-threatening, may or may not be symptomatic and may warrant palliative management, such as ocular lubricants or temporary interruption of contact lens wear.
Unanticipated Adverse Device Effect	Adverse events in a clinical trial that were not previously identified in the protocol in terms of nature, severity, or degree of incidence. An Unanticipated Serious Adverse Device Effect is an unanticipated adverse event that is serious in nature and caused by or associated with the device and is considered reportable.

Code	Condition	Reporting
Serious Adverse Events		
01	Presumed infectious keratitis or infectious corneal ulcer	Notify sponsor as soon as possible, within 24 hours ; IRB reporting as per requirements
02	Permanent loss of ≥ 2 lines of best spectacle corrected visual acuity (BSCVA)	
03	Corneal injury that results in permanent opacification within central cornea (6mm)	
04	Uveitis or Iritis (e.g. presence of anterior segment inflammation as described in ISO 11980, Annex B)	
05	Endophthalmitis	
06	Hyphema	
07	Hypopyon	
08	Neovascularization within the central 6mm of cornea	
00	Other serious event	
Significant Adverse Events		
11	Peripheral (outside central 6mm), non-progressive, non-infectious ulcer	Notify sponsor as soon as possible, within 5 working days ; IRB reporting as per requirements
12	Symptomatic corneal infiltrative event	
13	Superior epithelial arcuate lesions (SEALs) involving epithelial split	
14	Corneal staining \geq dense coalescent staining up to 2mm in diameter (e.g. moderate, ISO 11980 grade 3)	
15	Corneal neovascularization ≥ 1.0 mm vessel penetration (e.g. \geq ISO 111980 Grade 2), if 2 grade change from baseline	
16	Any temporary loss of ≥ 2 lines BSCVA for ≥ 2 wks	
17	Any sign and/or symptom for which subject is administered therapeutic treatment or which necessitates discontinuation of lens wear for ≥ 2 weeks	
10	Other significant event	

Non-significant Adverse Events		
21	Conjunctivitis (bacterial, viral or allergic)	Notify sponsor as soon as possible, within 5 working days ; IRB reporting as per requirements
22	Papillary conjunctivitis if \geq mild scattered papillae/follicles approximately 1mm in diameter (e.g. ISO 11890 Grade 2), if 2 grade change from baseline	
23	Asymptomatic corneal infiltrative events	
24	Any sign and/or symptom for which temporary lens discontinuation for > 1 day is recommended (if not already classified)	
20	Other sign and/or symptom warranting classification as a non-significant adverse event	

Normal or adaptive symptoms

Transient symptoms such as end-of-day dryness, lens awareness, itching or burning or other discomfort may occur with contact lens wear and may occasionally reduce wearing time. **These are not reported as adverse events unless in the investigator's opinion they are unexpected in nature, severe or have a high rate of occurrence.**

This clinical study will also ascertain satisfaction or preference with subjective attributes, such as comfort, vision or lens handling. Responses to these subjective questionnaires will not be considered as Adverse Events.

8.2 Procedures for Adverse Events

Treatment of an adverse event will depend on its nature and severity. Based on the clinical judgment of the investigator the subject may be referred to an ophthalmologist for treatment. The investigator will attempt to determine whether the reaction is related to the test device or a result of other factors. An Adverse Event Form will be completed for each adverse event. If both eyes are involved, a separate Adverse Event Form will be completed *for each eye*. Whenever possible, the adverse event will be photo-documented.

Expenses incurred for medical treatment as part of study participation will be paid by the sponsor (bills and prescription receipts kept). The subject must be followed until resolution and a written report completed indicating the subsequent treatment and resolution of the condition.

8.3 Reporting Adverse Events

All potential Serious and Unanticipated Adverse Device Effects that are related or possibly related to subject participation will be reported to the Principal Investigator and the sponsor within 24 hours

Confidential

18

of the investigator becoming aware of the event. The Principal Investigator will report the event to the IRB as soon as possible (by fax, mail/delivery, phone, or email). All fatal or life threatening events will be reported immediately to the IRB.

Significant and Non-Significant Adverse Events will be reported to the sponsor as soon as possible, but no later than 5 working days after the occurrence.

Sponsor contact details are:

Contact: Clinical Operations, CooperVision
Email: [REDACTED]
Phone: [REDACTED] or [REDACTED] / Fax: [REDACTED]
Address: [name]
[name]
[name]

8.4 Discontinuation from the Study

A subject's study participation may be discontinued at any time if, in the opinion of the sponsor or the investigator, it is in the best interest of the subject. All discontinuations will be fully documented on the appropriate study forms and the Discontinuation Form will be completed.

9 Device Malfunctions

A device malfunction means the failure of the device to meet its performance specification or otherwise perform as intended. *Any defective lens that is likely to cause or contribute to a Serious Adverse Event should be reported to the Principal Investigator and the sponsor **within 24 hours** of the investigator becoming aware of the malfunction.*

Other defective lenses should be reported to the Sponsor as soon as possible.

This clinical study will also ascertain satisfaction or preference with subjective attributes such as comfort, vision, or lens handling. Responses to these subjective questionnaires will not be considered as complaints or Device Malfunctions.

10 Statistical Analysis

